| MDSCs | Myeloid-derived suppressor cells |
| MUGA | Multiple Gated Acquisition scan |
| NCI | National Cancer Institute |
| | |

| NCI-CTCAE | National Cancer Institute-Common Terminology Criteria for Adverse Events | |
|-------------------|---|--|
| NSCLC | Non-small-cell lung carcinoma | |
| ORR | Objective response rate | |
| OS | Overall survival | |
| PBMC | Peripheral blood mononuclear cells | |
| PD | Progressive disease | |
| PD-1 | Programmed cell death protein 1 | |
| PD-L1 | Programmed cell death-ligand 1 | |
| PFS | Progression free survival | |
| PLT | Platelets | |
| PS | Performance Status | |
| PR | Partial Response | |
| PT | Prothrombin Time | |
| РТТ | Partial Thromboplastin Time | |
| RECIST | Response Evaluation Criteria in Solid Tumors | |
| SD | Stable Disease | |
| SF | Shortening Fraction | |
| STS | Soft Tissue Sarcoma | |
| Т3 | Tri-iodothyronine | |
| T4 | Thyroxine | |
| TILs | Tumor-infiltrating lymphocytes | |
| TNM | TNM Classification of Malignant Tumors (tumor/nodes/metastasis) | |
| TSH | Thyroid-Stimulating Hormone | |
| TTP | Time to Tumor Progression | |
| T _{regs} | Regulatory T cells | |
| ULN | Upper Limit of Normal | |
| VEGF | Vascular endothelial growth factor | |
| WBC | White Blood Cells | |

Roles and Responsibilities of Study Personnel:

[name], PhD: Principal Investigator of the study [name], MS, NP, MBA: President and CEO, SARC [name] [name], PhD, Research Manager [name]: Study Statistician

STUDY SYNOPSIS

Primary Objective

1. To determine the efficacy of pembrolizumab (MK-3475, SCH 900475) in patients with advanced sarcomas as measured by Objective Response Rate (ORR) using RECIST 1.1

Secondary Objectives

- 1. To determine the safety and tolerability of pembrolizumab in this patient population
- 2. To determine the Progression-Free Survival (PFS) by RECIST 1.1 and Overall Survival (OS) in this patient population
- 3. To determine the response rate as measured by the immune-related Response Criteria (ir-RC)

Exploratory Objectives

- 1. To determine the effect of pre-treatment PD-L1 expression levels on response rates and the role of PD-L1 expression as a predictive biomarker for clinical benefit
- 2. To determine the association of circulating regulatory T cells (Tregs) and Myeloid-Derived Suppressor Cells (MDSCs) at baseline and their changes while on therapy with clinical benefit
- 3. To perform immune monitoring in the circulation and in the tumor microenvironment while on therapy with pembrolizumab specifically, the frequency of circulating T cell populations, including NY-ESO-1 specific cytotoxic T cells, as well as T cell infiltration in available pre- and post- therapy tumor tissues will be assessed.

Trial Design

This is an open-label phase II study of pembrolizumab given at 200 mg IV every 3 weeks in patients with locally advanced or metastatic bone and soft tissue sarcomas.

Maximum Total Number of Patients

Initial enrollment was 86 patients: patients with soft tissue sarcomas and patients with bone sarcomas

In an expansion study, there will be an additional 60 patients enrolled to the soft tissue cohort: 30 patients with undifferentiated pleomorphic sarcoma and 30 patients with dedifferentiated or other high grade liposarcoma

Target Population

Patients with advanced refractory soft tissue or bone sarcomas

Efficacy Evaluations

Tumor measurements by CT/MRI imaging will be performed initially at 8 weeks and every 12 weeks subsequently - RECIST 1.1 will be the primary outcome measure and immune-related Response Criteria (ir-RC) will be a secondary outcome.

Duration of Participation

Each patient will participate in the trial from the time of Informed Consent Form (ICF) is signed through final protocol-specified contact. After a screening phase for eligibility, patients will receive pembrolizumab every 3 weeks. Treatment for patients that achieve stable disease (SD), a partial response (PR), or a complete response (CR) can continue for a maximum of 2 years total duration of treatment. At the discretion of the investigator, patients who have progressive disease (PD) but continue to achieve clinical benefit, may also continue on therapy for a maximum of 35 cyclestotal duration of treatment.

Safety Evaluations/ Concerns

Safety evaluations will be done according to CTCAE version 4.0 with special emphasis on immune-related adverse events (ir-AEs).

Correlative Studies

Blood for research studies will be collected prior to first study drug administration, at week 8, week 20 and week 32 and flow cytometry analyses will be performed to determine the presence of PD-1 expressing T cells, as well as the proportion of circulating Treg cells and MDSCs.

In the initial enrollment and in the first 20 patients of the expansion cohorts (UPS and LPS), preand post-treatment biopsies at week 0 and week 8 are mandatory. Biopsies at cycle 12 (week 34) and at progression are optional. PD-L1 expression, T cell infiltration, as well as suppressor subpopulations will be compared between pre and post-treatment biopsies.

Brief Statistical Design

In the initial enrollment of the study we tested the hypothesis that pembrolizumab has clinical activity in patients with advanced sarcoma. A patient will be classified as a treatment success if he/she achieves a Partial Response (PR) or better by RECIST 1.1. For each arm, an ORR of 25% will be considered clinically meaningful and a response rate less than 10% will be considered ineffective. In this study with a single stage design, we will accrue 40 patients in each arm. The treatment will be considered a success if 8 or more of 40 enrolled patients have a PR or better by RECIST 1.1. This design has a one-sided type I error of 4.2% and a power of 82% to detect a difference between 10 and 25% response rates. This design will also have 87% power to detect an improvement in the 4-months PFS rate from 20% to 40% with a one-sided type I error of 4%.

In the original 86 patient group, 80 patients were evaluable for objective response rate by

RECIST 1.1. Among 40 evaluable patients in the STS cohort, there were 7 partial responses with an ORR of 18%. Four partial responses were seen among 10 patients with undifferentiated pleomorphic sarcoma for an ORR of 40%. Two additional PRs were observed in the dedifferentiated/high grade liposarcoma cohort (2 out of 10) for an ORR of 20%. There was an additional PR seen in the synovial sarcoma cohort. Among 40 evaluable patients in the bone sarcoma cohort, there were 2 partial responses with an ORR of 5%. 1 PR was seen each in the dedifferentiated/high grade chondrosarcoma and osteosarcoma cohorts. Given the observed PRs in the UPS and dedifferentiated/high grade liposarcoma cohorts, we will enroll patients to expansion cohorts to include an additional 30 patients each (UPS and LPS) to further explore and confirm the activity of pembrolizumab.

In the study expansion, the response rates for undifferentiated pleomorphic sarcoma cohort and the poorly differentiated/dedifferentiated liposarcoma cohort will be analyzed separately. In each subtype cohort, we will analyze a total of 40 patients (10 from part 1 of the study and 30 from the expansion cohort). An objective response rate of 25% will be considered clinically meaningful and a response rate less than 10% will be considered lack of efficacy. The treatment will be considered a success if 8 or more of 40 enrolled patients have a PR or better by RECIST 1.1. This design has a one-sided type I error of 4.2% and a power of 82% to detect a difference between 10 and 25%.

At least 20 patients in each of the undifferentiated pleomorphic sarcoma and poorly differentiated/dedifferentiated expansion cohorts will have mandated biopsies for correlative analysis. The remaining 10 patients in each of the cohorts will not be required to obtain baseline and 8-week tumor biopsies, although archival tissue will be required for PD-L1 testing.

Table of Contents

| SARC Pro | otocol #: 0281 |
|---|---------------------------------------|
| Roles and | Responsibilities of Study Personnel:5 |
| STUDY S | СНЕМА |
| STUDY S | YNOPSIS7 |
| Secondary | 7 Objectives |
| Explorato | ry Objectives7 |
| Trial Desi | gn7 |
| Maximum | Total Number of Patients7 |
| Target Po | pulation7 |
| Efficacy E | valuations |
| Safety Eva | aluations/ Concerns |
| Correlativ | re Studies |
| Brief Stati | stical Design |
| 1. | OBJECTIVES16 |
| 1.1 | Primary Objective16 |
| 1.2. | Secondary Objectives |
| 1.3. | Exploratory Objectives16 |
| 2. | BACKGROUND16 |
| 2.1 | Study Disease16 |
| 2.2 | Study Agent - Pembrolizumab18 |
| Confidential P SARC028 v 5. 180CT2019 | |

Copyright©SARC (Sarcoma Alliance for Research through Collaboration)

| 2.3 | Background | 18 |
|-------------------|---|----|
| 2.4 | Clinical Rationale | 19 |
| 2.5 | General Investigational Approach | 20 |
| 2.6 | Chemical Properties | 20 |
| 2.7 | Structure | 21 |
| 2.8 | Physico-Chemical Properties | 21 |
| 2.9 | Pharmaceutical Formulation | 21 |
| 2.10 | Nonclinical Pharmacology | 21 |
| 2.11 | Affinity and Ligand Blockade of Pembrolizumab | 22 |
| 2.12 Syngeneic | In Vivo Efficacy of Analog Anti-Mouse PD-1 Antibody (as a Monotherapy) in Tumor Models | 22 |
| 2.13 | Non-Clinical Toxicology Summary of Results | 23 |
| 2.14 | Clinical Summary of Results | 23 |

1. OBJECTIVES

1.1 Primary Objective

1. To determine the efficacy of pembrolizumab (MK-3475, SCH 900475) in patients with advanced sarcomas as measured by Objective Response Rate (ORR) using RECIST 1.1

1.2. Secondary Objectives

- 1. To determine the safety and tolerability of pembrolizumab in this patient population
- 2. To determine the Progression-Free Survival (PFS) by RECIST 1.1 and Overall Survival (OS) in this patient population
- 3. To determine the response rate as measured by the immune-related Response Criteria (ir-RC)

1.3. Exploratory Objectives

- To determine the effect of pre-treatment PD-L1 expression levels on response rates and the role of PD-L1 expression as a predictive biomarker for clinical benefit
- To determine the association of circulating regulatory T cells (Tregs) and Myeloid-Derived Suppressor Cells (MDSCs) at baseline and their changes while on therapy with clinical benefit
- To perform immune monitoring in the circulation and in the tumor microenvironment while on therapy with pembrolizumab specifically, the frequency of circulating T cell populations, including NY-ESO-1 specific cytotoxic T cells, as well as T cell infiltration in available pre- and post- therapy tumor tissues will be assessed.

2. BACKGROUND

2.2 Study Agent - Pembrolizumab

Pembrolizumab formerly known as MK-3475 and SCH 900475 is a potent humanized IgG4 mAb with high specificity for binding to the PD-1 receptor, and thus inhibiting its interaction with PD-L1 and PD-L2. Based on preclinical *in vitro* data, pembrolizumab has high affinity and potent receptor blocking activity for PD-1. Overall, as of 03-Mar-2018, approximately 25,519 patients have been treated with pembrolizumab in clinical studies. Pembrolizumab has an acceptable preclinical safety profile and is FDA approved for the treatment of advanced melanoma, non-small cell lung cancer, squamous cell head and neck cancer, urothelial cancer, classical Hodgkin lymphoma, MSI-H or mismatch repair deficient colon cancer or solid tumors, and gastric/gastroesophageal junction adenocarcinoma.

2.3 Background

2.5 General Investigational Approach

Refer to current Investigator's Brochure for information on General Investigational Approach.

2.6 Chemical Properties

2.7 Structure

2.8 Physico-Chemical Properties

Refer to current Investigator's Brochure for Physico-Chemical Properties

2.9 Pharmaceutical Formulation

Refer to current Investigator's Brochure for information on Pharmaceutical Formulation

2.10 Nonclinical Pharmacology

2.11 Affinity and Ligand Blockade of Pembrolizumab

2.12 *In Vivo* Efficacy of Analog Anti-Mouse PD-1 Antibody (as a Monotherapy) in Syngeneic Tumor Models

[figure not shown]

Figure 1: Effect of Anti-PD-1 Monoclonal Antibody Monotherapy on Growth of MC38 Tumor

[Redacted]

[figure not shown]

Figure 2: Effects of Anti-PD-1 Monoclonal Antibody Monotherapy on Survival in MC38 Tumor Model

[redacted]

2.14 Clinical Summary of Results

2.15 Preclinical and Clinical Trial Data

Refer to current Investigator's Brochure for Preclinical and Clinical Trial data.

2.16 Rationale for the Trial and Selected Patient Population

This study is therefore a Phase II clinical trial to determine the preliminary clinical

efficacy of the anti-PD1 antibody pembrolizumab in patients with advanced sarcomas. Given the heterogeneity of advanced sarcomas, the study will have two separate arms that each encompasses sarcoma subtypes with similar anatomic primary sites and patterns of progression.

In the original 86 patient group, 80 patients were evaluable for objective response rate by RECIST 1.1. Among 40 evaluable patients in the STS cohort, there were 7 partial responses with an ORR of 18%. Four partial responses were seen among 10 patients with undifferentiated pleomorphic sarcoma for an ORR of 40%. Two additional PRs were observed in the dedifferentiated/high grade liposarcoma cohort (2 out of 10) for an ORR of 20%. There was an additional PR seen in the synovial sarcoma cohort. Among 40 evaluable patients in the bone sarcoma cohort, there were 2 partial responses with an ORR of 5%. 1 PR was seen each in the dedifferentiated/high grade chondrosarcoma and osteosarcoma cohorts.

Given the observed PRs in the UPS and dedifferentiated/high grade liposarcoma cohorts, we will enroll patients to expansion of both cohorts to include an additional 30 patients each (UPS and LPS) to further explore and confirm the activity of pembrolizumab.

2.17 Study Design

This is an open-label, Phase II study of pembrolizumab for patients ≥ 18 years of age with locally advanced, unresectable, recurrent, and/or metastatic soft tissue sarcomas, or ≥ 12 years of age for bone sarcomas. Patients will be assigned to one of 2 arms based on the sarcoma histologic subtypes: high grade aggressive soft tissue sarcomas (specifically leiomyosarcoma, poorly differentiated/de-differentiated liposarcoma, high grade pleomorphic undifferentiated sarcoma/MFH, MPNST and synovial sarcoma), and bone sarcomas (Ewing Sarcoma, osteosarcoma, and chondrosarcoma [de-differentiated or mesenchymal]). The patient population must meet all eligibility criteria specified in Section 3. A total of up to 80 patients will be included in the study. Patients will undergo screening evaluations to determine eligibility within 30 days of the first dose. Each 21 day dosing period will constitute a cycle.

Pembrolizumab is a potent humanized IgG4 anti-PD-1 mAb with high specificity of binding to the PD-1 receptor, thus perpetuates inhibition of PD-L1 and PD-L2 interaction. Based on preclinical *in vitro* data, pembrolizumab has higher affinity and receptor-blocking activity compared to other anti-PD-1 products in development. Pembrolizumab has an acceptable preclinical safety profile and is being advanced for clinical development as an IV immunotherapy for advanced malignancies. Pembrolizumab has been evaluated at 2 and 10 mg/kg every 3 weeks but a flat dose of 200 mg IV every 3 weeks will be utilized for further development.

Patients will be assessed for response (RECIST 1.1) by CT or MRI beginning 8 weeks (\pm 1 week) after treatment initiation and then every 12 weeks (\pm 1 week) until progression or treatment discontinuation, whichever occurs first. Treated patients will

be allowed to continue study therapy after initial RECIST 1.1 defined progression if they are assessed by treating physician to be deriving clinical benefit and tolerating study drug. Treating physician may consult with overall study PI as needed for help with assessing patient. Such patients should discontinue study therapy upon further evidence of progression.

In the initial enrollment and in the first 20 patients enrolled in each of the UPS and LPS cohorts, mandatory biopsies will be obtained during screening prior to initiation of therapy (week 0) and at 8 weeks (\pm 1 week) to coincide with radiologic disease assessment Additional tumor biopsies (optional) at cycle 12 (week 34) and at time of progression may be collected for easily accessible tumors. Surgical excisional biopsies or core biopsies are acceptable.

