5.6 Duration of Therapy

Treatment may continue until one of the following criteria applies:

- Patient achieves SD, PR, or CR and completes 35 cycles of treatment without unacceptable adverse event(s) (Section 6.1).
- Clinical or radiographic disease progression as defined by RECIST 1.1. Patient may be allowed to continue treatment after progression for a maximum of 35 cycles of treatment if they are deriving clinical benefit (refer to section 2.17).
- Patient decides to withdraw from the study
- General or specific changes in the patient's condition render the patient unacceptable for further treatment in the judgment of the site investigator
- Unacceptable adverse event(s) (Section 6.1)
- Need for > 2 dose delays due to toxicity
- Pregnancy in patient
- Patient is lost to follow-up.

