5.7 Duration of Follow Up

Patients will be followed for 30 days +/- 14 days after termination of study treatment or until death, whichever occurs first. Patients removed from study for adverse event(s) will be followed until resolution or stabilization of the adverse event.

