10.2 ON STUDY EVALUATIONS

Patients who have previously met laboratory inclusion criteria at screening may potentially receive Cycle 1 dose of medication even if laboratory studies drawn on

Cycle 1 day one do not meet the eligibility criteria. Study drug may be given as long as labs do not meet threshold for dose delay/schedule modification. Cycle visits will occur at each treatment visit (i.e. every 3 weeks) from study initiation. The following procedures will be performed during the treatment period:

- Physical exam, including weight, vital signs, ECOG performance status
- Administration of study drug
- Recording of adverse events
- Relevant laboratory evaluations, WBC, Hgb, Plt, ANC, Cr, K, Ca, ALT, AST, Total Bilirubin, alkaline phosphatase, PT (or INR), PTT, TSH, Free T4, T3
- Blood for research studies will be collected at week 8 (± 1 week) and then every 12 weeks (± 1 week) subsequently until patient completes 12 cycles
- Disease assessments will be performed at week 8 (± 1 week) and then every 12 weeks (± 1 week) subsequently
- Biopsy at week 8 (\pm 1 week) and optional biopsy may be collected at cycle 12.

NOTE: All studies can be obtained ± 3 days of stated time point unless otherwise noted.

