10.3 OFF TREATMENT EVALUATIONS

Final visit is to be performed at the time (or within 30 days +/- 14 days of removal from the treatment). Off treatment evaluations will include:

- Physical exam: height, weight vital signs, ECOG performance status
- Serum β -HCG or urine pregnancy test for women of childbearing potential
- Relevant laboratory evaluations, including CBC with differential and comprehensive serum chemistry panel
- Urinalysis
- PT (or INR) and PTT
- EKG
- Recording of adverse events (for unresolved adverse events, patients should be monitored for 30 days following the last dose of study drug)
- Extent of disease evaluation with appropriate radiographic procedures if not performed within 30 days of the final visit
- Off treatment Biopsy collected due to progression (optional).

Follow-Up:

Patients who complete study treatment should be followed for survival every 6 months. Patient will be contacted by phone at a minimum and survival status will be collected and documented. Survival status can also be assessed via patient's medical records or via certified letter.

STUDY CALENDAR

| | Pre- Study | Wk 1 | Wk 4 | Wk 7 | Wk 10 | Wk 13 | Wk 16 | Wk 19 | Wk 22 | Wk 25 | Wk 28 | Wk 31 | Wk ^K 34+ | Off Treatment ¹ |
|--|----------------|------------------|---------|---------|---------------------|----------|----------|----------|--------------------|----------|----------|---------------|------------------------|-------------------------------|
| Study Drug Admin ^a | | Х | Х | Х | Х | Х | Х | Х | Х | Х | Х | Х | Х | |
| Informed consent | Х | | | | | | | | | | | | | |
| History/Demographics | Х | | | | | | | | | | | | | |
| Physical exam ^b | Х | Х | Х | Х | Х | Х | Х | Х | Х | Х | Х | Х | Х | Х |
| CBC with Differential ^c | X f | Х | Х | Х | Х | Х | Х | Х | Х | Х | Х | Х | Х | Х |
| Comprehensive Serum Chemistry Panel ^d | X f | х | Х | х | Х | Х | Х | Х | Х | Х | Х | Х | Х | Х |
| TSH, FT4, T3 | X f | Х | Х | Х | Х | Х | Х | Х | Х | Х | Х | Х | Х | |
| PT (or INR) and PTT | X f | Х | Х | Х | Х | Х | Х | Х | Х | Х | Х | Х | Х | Х |
| Urinalysis | X f | | | | | | | | | | | | | Х |
| Serum or urine pregnancy test ^e | X f | | | | | | | | | | | | | Х |
| EKG | X g | | | | | | | | | | | | | Х |
| Archival Tumor Samples (FFPE) (only patients from expansion) | Х | | | | | | | | | - | | | | |
| Adverse event evaluation | | Χ- | | | | | | | | | | | X | Х |
| Biopsies | Х | X ^J - | | | | | | | | | | | X ^J | Х |

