11.1.6 Progression-Free Survival

Progression-Free Survival is defined as the duration of time from start of treatment to time of progression or death, whichever occurs first.

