13.3 Analysis of Secondary Endpoints

This design will also allow 87% power to detect an improvement in the 3-months PFS rate from 20% to 40% with a one-sided type I error of 4%.

Progression-free survival will be estimated by the product-limit method. PDL1 expression levels and baseline circulating T cell counts will be related to response via logistic regression, and to PFS via Cox regression. Changes in T cell counts will be related to outcome using appropriate landmarks. Several secondary objectives are clinical and include PFS, OS, ir-RC, and safety all of which will be analyzed taking into account the primary endpoint. All other correlative secondary objectives are exploratory as those data have not been previously reported in sarcoma and therefore will serve as hypothesis generating.

Mandatory pre/post biopsies will be performed for at least 20 patients enrolled in each of the expansion subtype cohorts. Because clear biomarkers for response to pembrolizumab remain to be determined and may not be histology specific, all samples will be evaluated as a single cohort for correlative assessments. PD1 expression on fresh biopsy tissue at both time points will be assessed. Cases will dichotomized into low/high expressers at baseline, and low/high expression changers from pre to post-treatment. Assuming an objective response rate of 10% in tumors with low expression at baseline, this will allow 90% power to detect a difference in objective response of 10% vs 40% using a two-sided 5% level test of proportions. Assuming up to 20% dropout between pre and post biopsies, if 64 patients have both pre and post biopsies, there will be 80% power to detect a difference in objective response of 10% vs 40% between low and high changers, using a two-sided 5% level test of proportions.

Any analyses by individual histologic subtypes will be exploratory only.

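### Tumor assessment ends with treatment and no PFS censoring rule is given, so patients who stop while deteriorating may be censored informatively; the 87% PFS power assumes complete landmark status

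*Combined protocol and SAP*

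**What the plan says.** Section 10.2 sets the scan schedule: "Disease assessments will be performed at week 8 (± 1 week) and then every 12 weeks (± 1 week) subsequently". Section 2.17 ends it "until progression or treatment discontinuation, whichever occurs first".

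Section 5.6 lists several reasons for stopping that need not involve progression on a scan, for example "Need for > 2 dose delays due to toxicity", withdrawal, or a change in condition that the investigator judges to rule out further treatment. It also lists clinical progression. Section 7.1.1.5 accepts clinical progression on symptomatic deterioration as a rare exception, and lets the investigator forgo further disease assessment in that case.

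The statements on what happens after treatment differ:

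- Section 10.3, final visit: "Extent of disease evaluation with appropriate radiographic procedures if not performed within 30 days of the final visit".
- Section 10.3, later: "Patients who complete study treatment should be followed for survival every 6 months". Read literally, this covers only those who complete treatment.
- Study calendar, note n: six-monthly survival calls, without that restriction.
- Section 5.7: "Patients will be followed for 30 days +/- 14 days after termination of study treatment or until death, whichever occurs first".
- Section 5.8: a patient who meets any section 5.6 criterion is removed from study.

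Section 1.2 sets PFS by RECIST 1.1 as a secondary objective. Section 11.1.6 defines it as the "duration of time from start of treatment to time of progression or death, whichever occurs first". Section 13.3 names the product-limit method and states: "This design will also allow 87% power to detect an improvement in the 3-months PFS rate from 20% to 40" per cent, at 4% one-sided error. The synopsis gives the same figures for 4 months. No section says how to treat a patient who stops, declines clinically or starts other therapy without RECIST progression.

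**The concern.** The product-limit method is valid when censored patients have the same outlook as those still under observation. Patients taken off treatment because they are declining do not. If they leave the risk set at their last clean scan, those who remain look healthier than the cohort and the PFS curve sits too high. The trial is single-arm and PFS is judged against a fixed 20% rate, so no control arm shares the bias.

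Separately, the power statement makes no allowance for unknown status at the landmark. The only loss allowance in section 13.3 is 20% for paired biopsies.

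**Working it through.** **1. The plan's own figure.** Inputs are n = 40 per arm (section 13.1) and p0 = 0.20, p1 = 0.40 (section 13.3). No PFS cut-off is stated, so it is inferred from P(X ≥ r | 40, p):

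| r | error at 0.20 | power at 0.40 |
|---|---|---|
| 12 | 8.75% | 92.9% |
| 13 | 4.32% | 87.1% |
| 14 | 1.94% | 78.9% |

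Only r = 13 fits the stated 4% and 87%. The same method reproduces the response design: P(X ≥ 8 | 40, 0.10) = 4.19% and P(X ≥ 8 | 40, 0.25) = 81.8%, against 4.2% and 82% stated. A count out of 40 requires a known status for each of the 40.

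**2. Censoring unrelated to prognosis.** Set the landmark at time 1. Let progression have hazard −ln(p) and stopping have hazard −ln(1 − d), where d is the probability of stopping by the landmark absent progression. Success is a Kaplan-Meier estimate of at least 13/40. Values of d are assumptions. Results from 8,000 simulated trials:

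| d | error | power |
|---|---|---|
| 0 | 4.4% | 87.5% |
| 5% | 3.7% | 83.9% |
| 10% | 3.9% | 82.9% |
| 20% | 4.0% | 81.9% |

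Some patients progress before they would have stopped, so the share actually censored is smaller than d. With λ = −ln(0.4) = 0.916 and μ = −ln(1 − d), it is μ/(λ + μ) × [1 − 0.4(1 − d)]. For d = 5% this is 0.0513/0.9676 × 0.62 = 3.3%. For d = 20% it is 0.2231/1.1394 × 0.68 = 13.3%.

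**3. Censoring just before progression.** This is the adverse limit. Suppose a share d of all patients is censored immediately before a progression that would have fallen before the landmark. Then a fraction f = d/(1 − p0) of the events is lost, the observed hazard is multiplied by (1 − f), and the estimate tends to p0^(1 − f). With p0 = 0.20:

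- d = 5%: f = 0.0625, and 0.20^0.9375 = 22.1%
- d = 10%: f = 0.125, and 0.20^0.875 = 24.5%
- d = 20%: f = 0.25, and 0.20^0.75 = 29.9%

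In simulation, the chance of wrongly reaching 13/40 is about 7% at d = 5% and 37–38% at d = 20%.

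**4. Timing.** Scans fall at weeks 8 and 20, each ± 1 week. Three and four months are about weeks 13 and 17, between the two. Only stops before the landmark bear on the 87%; later stops affect the rest of the curve.

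**The case against.** Several stronger readings are tempting, and the documents do not support them.

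- A reader might infer that patients who stop have no PFS information afterwards. Section 10.3 calls for a disease evaluation if none is recent, and deaths are PFS events where they are captured.
- A reader might infer that losing the week-20 scan undermines the landmark analysis. Progression first seen at week 19 or later is dated after month 3 or 4, so its loss removes no event from that estimate.
- A reader might count unknown status as failure, which gives power of 81%, 73% and 53% at 5%, 10% and 20% unknown. Counting it as success gives false-positive rates of 14%, 32% and 73%. The plan states neither rule, and the product-limit method uses censored patients, so these are not expected effects.

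It is also fair to say that section 7.1.1.5 makes clinical progression exceptional, that nothing in the documents shows that stopping for toxicity biases PFS upward, and that PFS is secondary: the success rule rests on response rate alone. Counting clinical progression in the main analysis would depart from PFS by RECIST 1.1.

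All of this stands, and it limits the size of the problem. It does not remove it. Kaplan-Meier does not correct informative censoring, the off-treatment scan is conditional and may be forgone in the patients who are declining, and death capture after discontinuation depends on which follow-up statement is applied.

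**Conclusion.** The concern holds for PFS, in two parts.

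First, ending assessment with treatment, without a censoring rule, leaves the RECIST PFS estimate open to upward bias from patients who stop for deterioration or start new therapy without a progression scan. That they would be censored is the natural reading of the definition and estimator, not a stated rule. The size cannot be derived from the documents. In the adverse limit, with an assumed 5–20% of patients affected, a true 20% rate would be estimated at about 22–30%.

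Second, the 87% is conditional on complete landmark status. Under an assumed 5–20% non-informative censoring it is about 82–84%, a loss of roughly 3 to 5 points. This rests on the inferred cut-off of 13 of 40 and on exponential times.

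The primary response-rate conclusion is not affected.

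**What to change.** No additional scans are needed.

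1. Keep PFS by RECIST 1.1 as defined, and state its censoring rules. Add a sensitivity analysis that counts documented clinical progression, discontinuation for deterioration, or start of new anti-cancer therapy as PFS events.
2. Record the dates of clinical progression and of new anti-cancer therapy at the existing off-treatment visit and six-monthly contacts.
3. State that the 87% assumes known landmark status for all 40, and give the lower figure beside it (about 82–84% under an assumed 5–20% non-informative censoring). Settle whether the landmark is 3 or 4 months.
4. Reconcile sections 5.7 and 10.3 and calendar note n, so that deaths after discontinuation are captured for all patients.

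The cost is two data fields, one further analysis, some wording and a slightly lower stated power. Continuing scheduled scans after discontinuation would reduce the problem at its source, but it adds procedures and is not required for the changes above.
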